6.4 Sample Size and Power

The proposed pilot study aims to collect data and estimate effect sizes measuring the effect of RV and RV+ when compared to the CC. Although, this pilot study is not powered to test for specific hypotheses regarding effect sizes, the sample size estimates were based on data obtained from our recently completely NIH funded study, ^{15,77} we estimated that a total of 72 BHS (24 per arm) and 312 students will participate in this study. With 24 BHS per arm, a two-sided 95% confidence interval in mean differences in content fidelity (CF) and process fidelity (PF between) RV or RV+ vs. CC will be produced. The minimum distance from the mean difference to the limits (margins of error) will equal to 9.3 (CF) and 0.35 (PF) with the estimated pooled standard deviations equal to 16 and 0.6 respectively. It is anticipated that 104 students per arm will be recruited (total = 312). Assuming a uniform attrition rate of 15%, a total of 268 evaluable students will be included in the final statistical analysis. With 89 students in each of the three study arms, a two-sided 95% confidence interval for mean differences in pre/post changes in student mental health symptoms and academic engagement between the two arms ((RV or RV+) vs. CC) will equal to 2.4 with estimated

pooled standard deviation equal to 8. Sample size justification was reported using PASS 13 software.⁷⁸

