3.2.1 Total Number of Study Sites/Total Number of Subjects Projected

We will conduct the pilot trial in 24 schools (8 in Control Condition, 8 in Remote Video, and 8 in Remote Video plus Coaching. We anticipate enrolling 24 administrators (1 per school), 72 behavioral health staff (3 from each school; 24 in CC, 24 in RV, 24 in RV+) and 312 students (104 in CC, 104 in RV, 104 in RV+). We expect that each school will have one staff member with prior mental health training (e.g., school counselor). This staff member will be expected to implement one of the group-EBPs. The two other staff will be tasked

with implementing CICO, as this intervention can be implemented by school staff without prior mental health training.^{62,63} We estimate that each school staff will conduct one CPP or CATS group with 5-6 students of similar developmental level (e.g., a group of 4th & 5th graders; 144 students total), and that each school staff in CICO will implement the intervention with 6 individual students of any school grade (144 students total).

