5.3 Implementation Fidelity

Content Fidelity to Tier 2 Group CBT (CPP & CATS). The Content Fidelity Checklist (CFC) reflects each activity component of the session agenda of the treatment protocols. Raters use a yes/no response scale to indicate whether or not the implementer covered a particular component. All GCBT sessions will be audio-recorded. 100% of sessions will be

coded by the first coder and approximately 20% of sessions will be randomly selected and coded by the second coder. Interrater reliability will be evaluated using Kappa coefficients⁶⁹

Process Fidelity to Tier 2 Group CBT (CPP & CATS). Process fidelity will be assessed via an adapted version of the rating system developed by Lochman and colleagues.⁷⁰ Ten items are rated on a scale of 0 to 4, with 0 being "Not At All" and 4 being "Very Often". Ratings are given on the extent to which school staff members delivered the intervention in an orderly fashion, using active learning strategies, etc. Exploratory factor analysis (EFA) yielded two factors on the 10-item scale. We will use the average *Total* and factor scores for analysis. 100% of sessions will be coded by the first coder and approximately 20% of sessions will be coded by the second coder. Interrater reliability will be evaluated using ICC.

Content Fidelity for CI/CO. Content fidelity for CI/CO will be assessed via the CI/CO Implementation Guide Fidelity Checklist (IGFC). The CI/CO IGFC is completed by the consultant (research staff) after school teams submit their completed CI/CO Implementation Guide. The IGFC is completed once and measures both the content and quality of the customized manual components for each school. The CI/CO IGFC/Content Measure is a 26-item measure of CI/CO customization of the following CI/CO components: (a) staff roles and responsibilities, (b) CI/CO process logistics, (c) daily progress report, (d) motivation system, (e) fading and self-monitoring procedures, (f) staff training procedures, and (g) data collection and progress monitoring procedures. Each item is scored according to completion status as "yes," "no," or "not applicable." The CI/CO IGFC/Content Measure will be scored by recording the frequency of "yes" scores over the frequency of "yes," and "no" scores.

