The CI/CO IGFC/Quality Measure, or part 2 of the IGFC/Content Measure, is also completed by the consultant (research staff) once teams submit their completed CI/CO Implementation Guide. The IGFC/Quality Measure is a 14-item measure of the quality of, or degree to which, team responses in customizing their respective CI/CO Implementation Guides are comprehensive, clear, feasible. Measurement entails examining team responses to items related to the (a) implementation roles and responsibilities, (b) implementation process, (c) motivation system, (d) fading and self-monitoring, (e) training/orientation of staff, mentors, students and families, and (f) data entry and progress monitoring. The IGFC/Quality Measure will be scored by recording a score of 0-3 for each item depending on whether or not the team response meets the criteria for being comprehensive, clear, and feasible (with 1 point awarded for each).

Process Fidelity to CI/CO. Process fidelity for CI/CO will be assessed with the Check-In/Check-Out Fidelity Checklist, a measure of the daily implementation of CI/CO. The CI/CO Fidelity Checklist is completed by the consultant (research staff) on a monthly basis after collecting the completed Daily Progress Report (DPR) student forms for each student involved in CICO. The Check-in/Check-Out Fidelity Checklist is an 11-item form that indicates whether or not students received daily CICO feedback based on the occurrence of the following: (a) student identification, (b) feedback date, (c) recorded goal, (d) behavioral expectations rated by the teacher for each period, (e) the number of daily points earned out of the number of possible points, (f) an indication of whether or not the goal was met, and (g) the signature of the teacher/mentor. The 11 items will be scored as "occurred" or "did not occur." The Check-In/Check-Out Fidelity Checklist will be scored by recording occurrence over occurrence-plus-non-occurrence and multiplying the decimal by 100.

Adoption Inventory (AI). The AI will track the number of times each intervention is used per school, per condition. This information will be collected one time at the end of the intervention via a REDCap survey.

Dosage Inventory (DI). The DI is an Excel tracking sheet exported from the website hosting the video modules listing the number of times and length of time each video module is accessed by BHS.

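### The fidelity margins in Section 6.4 (9.3 and 0.35) need 24 comparable staff scores per arm; under the plan's division of roles no fidelity instrument supplies more than 16, and three of the four supply 8

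*Combined protocol and SAP*

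**What the plan says.** Section 6.4 justifies the staff sample by precision, not power: "With 24 BHS per arm, a two-sided 95% confidence interval in mean differences in content fidelity (CF) and process fidelity" is to be produced for RV or RV+ against CC. The distances to the limits are given as "margins of error) will equal to 9.3 (CF) and 0.35 (PF"), with "estimated pooled standard deviations equal to 16 and 0.6 respectively". The 15% attrition allowance in the same section is applied to students only.

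Section 8.1.1 randomizes 24 schools, 8 per arm, with three staff in each. Sections 3.2.1 and 4.3 expect one of the three to have prior mental health training. Of that person, Section 3.2.1 says: "This staff member will be expected to implement one of the group-EBPs". The other two deliver CI/CO.

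Section 5.3 measures the two roles separately:

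- **Group content fidelity (CPP and CATS only):** a yes/no checklist of session components.
- **Group process fidelity (CPP and CATS only):** "Ten items are rated on a scale of 0 to 4".
- **CI/CO content fidelity (IGFC):** "The IGFC is completed once and measures both the content and quality of the customized manual components for each school".
- **CI/CO process fidelity:** a monthly checklist based on students' daily progress forms, which "will be scored by recording occurrence over occurrence-plus-non-occurrence and multiplying the decimal by 100".

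Section 6.1 makes content and process fidelity the primary staff endpoints. No section defines a single content or process score that combines the group and CI/CO instruments.

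**The concern.** A margin based on 24 per arm presumes that each of the 24 staff contributes one score on a common scale and that the scores are independent. The role split and the instruments do not allow this. Group fidelity exists only for group leaders, the IGFC is a property of the school, and the CI/CO process checklist is a percentage rather than a 0 to 4 rating.

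Precision is the only justification offered for the staff sample size. Section 6.4 gives estimation of effect sizes as the pilot's purpose, and Section 6.3 looks ahead to a larger trial. A reader planning that trial would expect fidelity contrasts considerably tighter than the instruments are likely to give.

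**Working it through.** **Inputs.** From Section 6.4: 24 staff per arm, SD 16 (content), SD 0.6 (process), two-sided 95%. From Section 8.1.1: 8 schools per arm. From Sections 3.2.1 and 4.3: one group leader and two CI/CO staff per school.

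**Formula.** For n scores per arm, half-width = t(0.975, 2n − 2) × SD × √(2/n).

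**Step 1: reproduce the plan.** With n = 24, df = 46 and t = 2.013:

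- Content: 2.013 × 16 × √(2/24) = 9.30
- Process: 2.013 × 0.6 × √(2/24) = 0.349

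Both round to the stated figures, so the calculation is a two-sample t interval on 24 independent scores per arm.

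**Step 2: count the scores.**

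| Instrument | Scores per arm |
|---|---|
| Group content checklist | 8 × 1 = 8 |
| Group process rating (0 to 4) | 8 × 1 = 8 |
| CI/CO IGFC | 8 (one per school) |
| CI/CO process checklist (0 to 100) | at most 8 × 2 = 16, in 8 schools |

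This assumes one score per implementer, averaged over sessions or months, and one IGFC score per school. Combining the two content instruments would still give only 8 + 8 = 16 distinct scores.

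**Step 3: check the role split against the student numbers.** The abstract gives groups of 5 and 4 CI/CO students per CI/CO staff member. One leader and two CI/CO staff then serve 5 + 2 × 4 = 13 students per school, and 24 × 13 = 312, the planned total. If all 72 staff ran groups of 5, 72 × 5 = 360 students would be needed for groups alone. The 144 group students in Sections 3.2.1 and 4.3 equal 24 × 6, one group per school.

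**Step 4: 8 scores per arm.** With df = 14, t = 2.145 and the plan's SDs:

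- Content: 2.145 × 16 × √(2/8) = 17.2
- Process: 2.145 × 0.6 × √(2/8) = 0.64
- Ratio to the stated margins: 17.16/9.30 = 1.85

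To recover the stated margins with 8 per arm, the SDs would have to be 9.3/(2.145 × 0.5) = 8.7 and 0.35/(2.145 × 0.5) = 0.33.

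**Step 5: CI/CO process checklist, 16 per arm.** The plan gives no SD for it, so SD 16 is used only to obtain ratios.

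- Independent scores, df = 30, t = 2.042: 2.042 × 16 × √(2/16) = 11.55, ratio 1.24.
- School-based df = 14, two staff per school, design effect 1 + ICC: 2.145 × 16 × √(2(1 + ICC)/16) = 12.1 at ICC 0 and 17.2 at ICC 1, ratios 1.3 to 1.85. The ICC is not in the documents, so the full range is shown.

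**Step 6: the most favourable case.** Suppose all 24 staff did share a common score. With school-based df = 14 and three staff per school, the half-width is 2.145 × SD × √(2(1 + 2 × ICC)/24). For content this is 9.9 at ICC 0 and 12.5 at an assumed ICC of 0.3. For process it is 0.37 and 0.47.

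**The case against.** **Text that supports 24.** The abstract says that all staff run a group, and Section 3.2.1 has a sentence attributing a group to each member of school staff. Read literally, that gives 24 group leaders per arm, the n in Section 6.4. The counts in Step 3 and the explicit role assignment in Sections 3.2.1 and 4.3 weigh against it. Even so, the text is not consistent throughout: 144 + 144 = 288 is not 312, and 48 CI/CO staff with 6 students each would be 288 CI/CO students, not 144. The role split is the better-supported reading, but the sections need reconciling.

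**The SDs.** They come from an earlier study, and Section 6.4 names neither the instrument nor the level. If they describe single sessions, averaging over the 8 CATS or 12 CPP sessions would give smaller implementer-level SDs and narrower intervals. This stands, so 17.2 and 0.64 are conditional figures.

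**Clustering and timing.** Section 6.3 plans to explore multilevel and GEE models for staff within schools, and Section 6 says the SAP will be updated before database lock. Both are to the plan's credit, but neither changes the figures in Section 6.4 or creates additional scores.

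**Pilot status.** Section 6.4 disclaims power for specific hypotheses, and nothing is decided on these margins. This lowers the severity.

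**Stronger readings that a reader might infer.**

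- That every fidelity instrument yields only 8 scores per arm. The CI/CO process checklist covers two staff per school and can yield up to 16.
- That an SD of 0.6 can belong only to the 0 to 4 rating. It fits that scale far better than a percentage, but Section 6.4 does not name the scale, so this is an inference.
- That the plan intends to pool group and CI/CO scores. No section says so.
- That the arithmetic is wrong. It reproduces; the input n is what does not match the design.

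**Conclusion.** The concern holds under the role split in Sections 3.2.1 and 4.3. The stated margins require 24 comparable, independent scores per arm, and no fidelity instrument supplies them. Both content measures and the group process rating supply 8; the CI/CO process checklist supplies at most 16, clustered in 8 schools.

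For the group measures the half-widths are about 17.2 and 0.64 in place of 9.3 and 0.35, on the assumption that SDs of 16 and 0.6 describe implementer-level group scores. These figures also treat CPP and CATS leaders as one set. If results were reported by protocol with, say, 4 leaders per arm, the same formula with df = 6 (t = 2.447) gives 2.447 × 16 × √(2/4) = 27.7 and 2.447 × 0.6 × √(2/4) = 1.04. For the CI/CO process checklist only the relative widening in Step 5 can be stated, because no SD is given. Loss of staff would widen all of these further.

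This should be fixed before the SAP is finalized. It does not invalidate the pilot and is not an argument that the sample is too small for its purpose.

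**What to change.** Rewrite the fidelity part of Section 6.4 by instrument:

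- **Group content and group process:** 8 leaders per arm, with margins of about 17.2 and 0.64 if the SDs of 16 and 0.6 are confirmed as implementer-level values for these scales. If they are not, substitute the correct SDs.
- **CI/CO content (IGFC):** 8 schools per arm, with its own SD.
- **CI/CO process:** up to 16 staff per arm in 8 schools, with an SD on the percentage scale, school-based degrees of freedom and a stated range of ICC.

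State whether CPP and CATS leaders are analysed together, and whether any loss of staff is allowed for. Keep the group and CI/CO instruments separate unless a common score and its SD are defined in advance. Reconcile the abstract and the all-staff sentence in Section 3.2.1 with Section 4.3 on who conducts groups, together with the student totals.

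The cost is a revised paragraph and a less favourable stated precision. Recruitment and data collection are unchanged.

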This study is designed to test the effectiveness of initial training compared to remote video training and remote video training plus coaching to train BHS to implement EBPs. Each school will be randomly assigned to receive one of three training supports: (a) Initial training (CC) (b) Initial training, plus video (RV) or (c) Initial training plus video, plus remote coaching (RV+). BHS in the RV+ condition will receive consultation from a CHOP consultant regarding implementation of EBPs, whereas BHS in the RV condition will be given access to the asynchronous training video modules. Participants in all three conditions will receive treatment manuals for the interventions they have chosen. The EBPs to be implemented by the BHS include: Coping Power Program (CPP), CBT for Anxiety Treatment in Schools (CATS), and Check-in/Check-out (CI/CO). All BHS will conduct one CPP or CATS group with 5 students of similar developmental level (e.g., a group of 4th &

5th graders), and that each school staff in CI/CO will implement the intervention with 4 separate individual students of any eligible school grade.

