5.4 Student Outcome Measures

Parent, teacher, and student measures will be collected at pre-treatment and post-treatment of the pilot trial to assess changes in mental health symptoms and academic engagement.

Mental health symptoms. The BASC-3 ⁵⁵ is a 138-item, 4-point, Likert-type rating scale for assessing parental report of child mental health functioning, standardized for ages 2.5 to 18 years. The BASC-3 has excellent psychometric properties. ⁵⁵ The BASC-3 (*Aggression, Conduct Problems, and Anxiety* scales) will be administered at pre- and post-treatment for children who participate in CPP, CATS or CICO. Parents will complete the paper and pencil version of the BASC-3⁵⁵ over the phone with a research assistant or they may complete electronically. When this measure is administered to Spanish proficient parents, the research assistant will call language services to connect to an interpreter and the measure will be completed by phone.

Student academic engagement. The Engagement versus Disaffection with Learning: Teacher Report (EvsD) ⁷¹ will be completed by teachers for all children receiving Tier 2 interventions. This is a 20-item, four-point instrument with four sub-scales: (a) *Behavioral Engagement*, (b) *Emotional Engagement*, (c) *Behavioral Disaffection*, and (d) *Emotional Disaffection*. The survey will be completed by hand or electronically via REDCap survey. We will use the average score for each of the four scales at pre- and post-participation in CPP, CATS or CICO.

Externalizing and Internalizing Problems: Children will complete The Behavior and Feeling Survey-Your Report (YFS-SR). The YFS-SR is a brief (10 items) measure of internalizing and externalizing problems rated on a 5-point scale. The YFS-SR has excellent psychometric properties and it is sensitive to change. ⁵⁰ The YFS-SR provides three scores (Internalizing, Externalizing, Total). The measure will be completed at pre- and post-treatment for children who participate in group CBT or CICO.

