8 STUDY ADMINISTRATION

8.1 Treatment Assignment Methods

8.1.1 Randomization

The 24 invited schools will be recruited from 2 geographic locations (urban/rural). Schools will be stratified based on the geographic location and a computer-generated block randomization list will be prepared to randomize the 24 schools in a 1:1:1 ratio to either RV, RV+ or CC (8 schools/arm) stratified by geographic locations (urban/rural). The block randomization with varying will ensure equal number of schools in each arm and eliminate the predictability of schools' assignment. It is estimated that a total of 72 behavioral health staff (3 staff per school- 24 per arm) and 312 students (13 students per school- 104 per arm) will participate in this randomized parallel groups pilot study.

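### The single student margin of 2.4 (SD 8) leaves out school clustering, so it is too narrow for the BASC-3 scales unless the ICC is near zero, and its SD cannot apply to the averaged engagement scales, for which it is far too wide.

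*Combined protocol and SAP*

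**What the plan says.** Section 6.4 states that the pilot is not powered for specific hypotheses and supports its sample size with confidence-interval widths instead. For students it promises "a two-sided 95% confidence interval for mean differences in pre/post changes in student mental health symptoms and academic engagement", comparing RV or RV+ with CC. With 89 students per arm, the margin for "changes in student mental health symptoms and academic engagement between the two arms ((RV or RV+) vs. CC) will equal to 2.4 with estimated" a pooled SD of 8. One margin and one SD therefore serve all seven primary student scales in section 6.1: three from the BASC-3 (Aggression, Conduct Problems, Anxiety) and four for academic engagement.

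Section 8.1.1 plans to "randomize the 24 schools in a 1:1:1 ratio", which is 8 schools per arm with 13 students each, and section 6.2 names the school as the unit of randomisation. Section 6.4 mentions no ICC and no design effect. Section 6.3 starts with t-tests on change scores and a mixed model with a student-level random effect. School nesting is to be explored, by a multilevel model and by GEE.

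On the engagement measure, section 5.4 says "This is a 20-item, four-point instrument with four sub-scales" and "We will use the average score for each of the four scales at pre- and post-participation".

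On counts, section 6.4 applies 15% attrition to 312 students and reports that "a total of 268 evaluable students will be included in the final statistical analysis". The abstract has groups of 5 and says each CI/CO staff member "will implement the intervention with 4 separate individual students of any eligible school grade". Section 3.2.1 has groups of 5 to 6 (144 students) and says each CI/CO staff member "will implement the intervention with 6 individual students of any school grade (144 students total"). Section 4.3 repeats the 144 and 144.

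**The concern.** Interval width is the only quantitative justification for the sample size in section 6.4, so the stated width ought to be one the design can deliver. Two features suggest that it is not.

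First, students in a school share the randomised assignment, a handful of implementers and, for the group programmes, the same group. Teachers nominate the students and also rate engagement. Changes within a school may well be correlated, and any positive correlation widens the interval.

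Second, an SD of 8 looks incompatible with a score that is an average on a four-point instrument.

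At stake is what a reader, or the planners of the anticipated larger study, would take from the pilot: too much confidence in the BASC-3 estimates, and a margin for engagement that describes nothing on the scale to be analysed.

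**Working it through.** **Inputs from the documents.** 95% two-sided interval, n = 89 evaluable per arm, SD = 8, stated margin 2.4 (section 6.4); 8 schools per arm (section 8.1.1); engagement scored as an average on a four-point instrument (section 5.4).

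**Assumed, because the documents give no value.** ICC of the change score: 0.02, 0.05 and 0.10, with 0.20 as an outer value. Equal school sizes. Engagement responses scored in unit steps, so an average spans 3 points whatever the anchors.

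**1. Reproduce the stated margin.** Half-width = t × SD × √(2/n). With t(176) = 1.974 and √(2/89) = 0.1499, this is 1.974 × 8 × 0.1499 = 2.37, which rounds to 2.4. The same formula gives the staff margins: t(46) = 2.013, so 2.013 × 16 × √(2/24) = 9.30 and 2.013 × 0.6 × √(2/24) = 0.349, against 9.3 and 0.35 stated. Section 6.4 therefore uses two-sample intervals for independent observations throughout.

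**2. Add clustering, SD 8.** Evaluable students per school: m = 89/8 = 11.125. Design effect: DEFF = 1 + (m − 1) × ICC = 1 + 10.125 × ICC. Half-width = t × 8 × 0.1499 × √DEFF. School-based degrees of freedom for a two-arm comparison are 16 − 2 = 14, with t = 2.145.

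| ICC (assumed) | DEFF | Half-width, 176 df | Half-width, 14 df |
|---|---|---|---|
| 0 | 1.00 | 2.37 | 2.57 |
| 0.02 | 1.20 | 2.60 | 2.82 |
| 0.05 | 1.51 | 2.90 | 3.16 |
| 0.10 | 2.01 | 3.36 | 3.65 |
| 0.20 | 3.02 | 4.12 | 4.47 |

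Relative to 2.37, ICCs of 0.02 to 0.10 widen the interval by 10% to 42% through clustering alone. With 14 df as well, the widening is 19% to 54%. On 176 df the margin stops rounding to 2.4 once it reaches 2.45: (2.45/2.367)² = 1.0716, and 0.0716/10.125 gives an ICC of about 0.007.

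**3. Bound the engagement SD.** An average that spans 3 points can change only within −3 to +3. The largest SD of such a variable is 3, reached when half the students move by +3 and half by −3; as a sample SD with n = 89 it is 3.02. An SD of 8 is more than 2.5 times that ceiling. At the ceiling the unclustered margin is 1.974 × 3 × 0.1499 = 0.89. With clustering at ICC 0.10 it is at most 1.26 (176 df) or 1.37 (14 df), and at ICC 0.20 at most 1.68 (14 df).

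For illustration only, an assumed SD of 0.5 to 1.0 gives 0.15 to 0.30 unclustered, and at ICC 0.10 gives 0.21 to 0.42 (176 df) or 0.23 to 0.46 (14 df).

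**4. Check the counts.** 312 × 0.85 = 265.2, and 104 × 0.85 = 88.4 per arm. With 88 per arm the margin is 2.38, so the difference from 268 has negligible effect. On the abstract's figures, 5 + 4 + 4 = 13 per school and 24 × 13 = 312. The subtotals in sections 3.2.1 and 4.3 give 144 + 144 = 288, which is 12 per school.

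**The case against.** The strongest reply is that 2.4 is correctly calculated and matches the t-tests on change scores that section 6.3 names first. Clustering is acknowledged there through a multilevel model and GEE, the documents supply no ICC, and no test or decision rule depends on the margin. Section 6.4 disclaims power, and section 6 says the SAP will be updated before database lock.

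Much of this stands. A reader might infer that 2.4 is an arithmetic slip, or that it is shown to be wrong for all seven scales. The documents do not support either. The arithmetic is right under its assumption, and for BASC-3 the size of the shortfall depends on an ICC that nobody has stated. Near zero it is small: 2.37, or 2.57 on 14 df. The choice of 14 df is also a convention. One model for all 24 schools in three arms would have 21 df (t = 2.080), giving 2.73, 3.06 and 3.54 at the three ICCs.

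On engagement, it can be said that SD 8 would be possible for a sum score. If the 20 items split equally, five items per sub-scale allow changes within ±15. But section 5.4 specifies averages, so the SD is impossible as the plan is worded.

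The pilot label does not dispose of the point. Section 6.4 says the aim is to estimate effect sizes and offers 2.4 as the margin of those estimates. Exploring clustering in the analysis does not put it into that figure. An unclustered interval of about ±2.4 would have less than 95% coverage whenever the ICC is positive.

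**Conclusion.** The point holds as a should-fix. The single student margin combines two faults that run in opposite directions.

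- **BASC-3, three scales.** With SD 8, 2.4 is too narrow unless the ICC is near zero. At ICCs of 0.02 to 0.10 the half-width is 2.60 to 3.36 on 176 df or 2.82 to 3.65 on 14 df. The omission of clustering is certain; its size rests on the assumed ICCs and on equal school sizes.
- **Engagement, four scales.** SD 8 cannot apply to a score averaged on a four-point instrument. The unclustered margin is at most about 0.9, so 2.4 is far too wide. This rests on the wording of section 5.4 and on unit-step scoring, not on any outside figure.

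A reader might also infer that the correction makes all the student precision look worse. It does not: the BASC-3 margin grows and the engagement margin shrinks. Nor do the documents show that the trial needs more students. Read literally, six CI/CO students for each of 48 staff would be 288, or 432 with 144 group students. Section 3.2.1 itself prints 144 for CI/CO and 312 overall, so 432 is not a planned total. The count conflict and the 268 are minor consistency matters and do not alter the 2.4.

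**What to change.** In section 6.4:

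1. Restate the 2.4 sentence for the BASC-3 scale scores only. State an ICC range with its source or as an assumption, the design effect for about 11 evaluable students per school, and school-based degrees of freedom, naming the convention. The table above shows the form this could take; its ICCs are illustrative and should be replaced by the sponsor's own.
2. Give academic engagement a separate SD and margin on the averaged scale, also with clustering. If sum scores are intended instead, change section 5.4 to say so.
3. Replace 268 with about 265 (88.4 per arm before rounding), or state the attrition rate that gives 268.
4. Use one per-school count in the abstract and in sections 3.2.1, 4.3, 6.4 and 8.1.1. Of the breakdowns given, only 5 + 4 + 4 reproduces 312; the sponsor should decide which is intended and carry it into the design effect.

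The cost is protocol wording. The stated BASC-3 precision becomes less favourable, and no extra students are required.
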